10.2 Planned recruitment rate

We aim to recruit 10 participants into the study each month.

10.3 Statistical analysis plan

CONFIDENTIAL

IRAS: 240464

Eudra CT number 2018-000963-99

10.3.1 Summary of baseline data and flow of patients

Mean (SD) age, body mass index, baseline serum uric acid, gout disease duration, serum creatinine,

and n (%) female, with tophi will be used to assess the suitability of randomisation.

10.3.2 Primary outcome analysis

N (%) will be used to assess drop-out rate.

10.3.3 Secondary outcome analysis

Mean (SD) and n (%) will be used to assess secondary outcomes. Mean difference in number of flares between the two arms, and pooled SD will be used to estimate the effect size of the intervention.

10.4 Subgroup analyses

As this is a feasibility study, we do not intend to perform subgroup analysis.

10.5 Adjusted analysis

As this is a feasibility study, we do not intend to perform adjusted analyses.

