4. TRIAL DESIGN

Study design: single centre randomised double blind placebo controlled parallel arm feasibility study

Study population: patients with gout eligible to start on urate lowering treatment according to the British Society for Rheumatology Guidelines

Randomisation: 1:1

Randomisation time: Randomisation will occur once the results of screening blood tests performed at the screening visit are reviewed and eligibility and ongoing consent is confirmed.

Study groups:

Group A: placebo capsules (4 gm olive oil/day)*

Group B: omega-3 fatty acid capsules (4 gm/day; containing 3.36 gm of omega-3 fatty acids)

After four weeks participants in both arms will be commenced on uptitrated urate lowering treatment

as recommended by the British Society for Rheumatology Guidelines

Olive oil is filled in the placebo as it not known to have an immunosuppressive effect on gouty inflammation.

Final efficacy visit: week 28

Final safety visit (telephone call): week 32

Primary endpoint: week 28 visit of last patient

Secondary endpoints: complete data analysis

Data will be collected in paper case report forms and stored on secured servers that are backed up on a daily basis. Data analysis will be performed using STATA version 15. Staff entering study data into the CRF and into the database will be trained in data entry. Trial manager will perform data verification

CONFIDENTIAL

Page 30 of 77

IRAS: 240464

Eudra CT number 2018-000963-99

on a monthly basis on 10% of the data entered and any discrepant data will be checked against the source data. Data will be archived by the Nottingham University Hospitals NHS Trust as per SOP RES-028 for at least 25 years. Sponsor's data protection procedures will apply. Violations of eligibility criteria will be deemed to be a serious GCP breach and reported as such. Other deviations from protocol will be assessed and classified by the CI. Major protocol deviations (violations) from protocol will lead to exclusion of a participant from the per protocol set.

The database will be locked at the end of the study after cross validation of 5% of entered data against source data has occurred successfully, and all biologically implausible data are cross checked against source data.

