7.3 The randomisation scheme

Patients will be randomized into two arms using randomly permuted block sizes. Stratification will be used to evenly balance participants with contra-indications to allopurinol prescription at randomisation. This is as participants intolerant to allopurinol will be commenced on febuxostat which has a greater risk of precipitating flares than slow dose escalation of allopurinol.

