7.6 Baseline data

Baseline visit: The study participant will see a Research Metrologist at the baseline visit. We anticipate this visit to last for 60-90 minutes.

At this visit, the Metrologist will confirm willingness to continue on the study and then enquire about the age at first gout flare, number of flares in previous 12 months, collect information about the current medications, confirm data on co-morbidity collected in the screening questionnaire, assess previous gout treatment, conduct a targeted musculoskeletal assessment, and measure height, weight, and blood pressure.

The participant will complete the gout activity questionnaire and the short-form 36 version 2 quality of life questionnaire. Approximately 5 ml blood will be collected for measuring omega-3 fatty acids, and, if **CONFIDENTIAL** Page **38** of **77**

Eudra CT number 2018-000963-99

the participant agrees, approximately 10ml blood will be collected and stored for future research including genetic research.

The participants will be given a flare diary to collect information about the severity of flares of gout. The participants will be randomised prescribed and dispensed a 14 week supply of IMP or matching placebo. The participants will also be given a supply of urate lowering treatment (typically allopurinol 100 mg/day or febuxostat 80 mg/day if allopurinol is contra-indicated or has previously caused sideeffects) not to be started until the 5th week and a rescue pack containing prednisolone tablets 30 mg/day and omeprazole capsule 20 mg/day for 1 week to be taken during a gout flare. In case corticosteroids are contraindicated, the rescue pack will contain tablet Naproxen 500 mg twice a day. and omeprazole 20 mg/day for 1 week with. The participants will be specifically asked not to start urate lowering treatment until day 29. They will be contacted by phone, or text 2-3 days prior to day 29 as a reminder.

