10 STATISTICS AND DATA ANALYSIS

10.1 Sample size calculation

The main outcome of this study is dropout rates. A sample size of 60 will be able to estimate a dropout rate of 20% or higher to within a 95% confidence interval of +/- 10%.

The other purpose of this study is to calculate the sample size of the main trial, and to get a signal of efficacy of omega-3 fatty acids. Such a study does not require a formal sample size calculation, but the sample size for a pilot trial can be justified based on published rules of thumb and expected effect size. Several rules of thumb exist and suggest that a two arm pilot trial should have between 24 and 70 participants to allow calculation of the sample size of a definitive trial (58-61). Others recommend that a pilot randomized controlled trial should have 10, 14 and 24 participants in each arm if the treatment is expected to have an effect size of 0.8, 0.5, and 0.2 respectively, using the 80% CI approach in order to accurately estimate the sample size of the main trial (61). However, the ES of omega 3 fatty acids for preventing flares of gout is not known. Thus, we propose to include 60 participants (allowing for a c. 20% drop out rate) in this study to allow us to estimate the SDp with a reasonable degree of certainty, even if the effect size is 0.2 (61).

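### The planned flare effect size uses neither the stratification factor nor the baseline flare count, so it gives up some precision and a pre-specified residual SD for phase III

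*Protocol*

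**What the plan says.** Five places in the protocol bear on this.

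- **Section 7.3 (randomisation).** "Stratification will be used to evenly balance participants with contra-indications to allopurinol prescription at randomisation". The reason given is that participants who cannot take allopurinol will receive "febuxostat which has a greater risk of precipitating flares than slow dose escalation of allopurinol". The protocol thus treats the factor as prognostic for the flare outcome.
- **Section 7.6 (baseline data).** The baseline visit records the "number of flares in previous 12 months".
- **Section 10.3.1 (baseline summary).** The variables for judging the randomisation are age, body mass index, serum uric acid, disease duration, creatinine, sex and tophi. Allopurinol contra-indication and prior flares are not among them.
- **Section 10.3.3 (secondary outcomes).** The effect size comes from the mean difference in flares between arms and the pooled SD. No test, standard error or confidence interval is named.
- **Section 10.5.** "As this is a feasibility study, we do not intend to perform adjusted analyses".

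Section 3.1 makes the phase III sample size and the flare signal objectives (e) and (f). Section 10.9 says that departures from the agreed analysis plan will be reported as post hoc.

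**The concern.** The design treats one variable as important enough to stratify on, and the analysis then leaves it out. The count of flares in the year before entry is a natural predictor of flares on study. It is collected from everyone and is also left out. Section 10.5 settles this as a stated choice, so it is not a detail waiting for the SAP.

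Objectives (e) and (f) are what is at stake. With about 24 analysed per arm, the arms can differ by chance in flare history, and a raw comparison carries part of that difference into the signal. If phase III is to be analysed with adjustment, its sample size depends on the residual SD, or equally on the correlation between prior and on-study flares. This study could estimate both from data it already collects, but the planned analysis produces neither. Because the balance table omits both variables, the report might not show whether stratification worked or whether flare history differed between arms.

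**Working it through.** **Inputs from the protocol.** Total 60 with 1:1 allocation (sections 4 and 10.1). The rule of thumb in section 10.1 is "10, 14 and 24 participants in each arm if the treatment is expected to have an effect size of 0.8, 0.5, and 0.2 respectively", and the total is set "allowing for a c. 20% drop out rate". Section 2 gives SDs of flares in the preceding 12 months, from another trial's baseline data: 2.62 in supplement users and 5.44 in non-users.

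**Assumptions, not in the protocol.** Correlation r between prior and on-study flares: 0.2 to 0.6. Share q of participants with an allopurinol contra-indication: 5% to 20%. Difference D in flares between strata: 0.3 to 0.8 within-stratum SDs.

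**1. The plan's own figure.** 24 per arm is 48, and 48 / (1 − 0.20) = 60. For dropout, 1.96 × √(0.2 × 0.8 / 60) = 0.101, or 10.1 points at a 20% rate. The total of 60 is reproduced, and neither step depends on how flares are analysed.

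**2. Precision of the raw flare difference.** On the SD scale, SE = √(2/24) = 0.289, so the 95% half-width is 1.96 × 0.289 = 0.57 SD.

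**3. Precision after adjusting for prior flares.** Adjusted SE = 0.289 × √(1 − r²), and the variance cut is r².

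| r | Adjusted SE | Variance cut |
|---|---|---|
| 0.2 | 0.283 | 4% |
| 0.3 | 0.275 | 9% |
| 0.4 | 0.265 | 16% |
| 0.5 | 0.250 | 25% |
| 0.6 | 0.231 | 36% |

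At r = 0.5 the half-width falls from 0.57 to 0.49 SD.

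**4. Chance imbalance in flare history.** The between-arm difference in mean prior flares has SE 5.44 × 0.289 = 1.57 flares, or 2.62 × 0.289 = 0.76 with the smaller SD. A gap of at least 1.1 flares (4.17 − 3.07, the contrast in section 2) has a probability of about 48% with SD 5.44 and about 15% with SD 2.62. Only a fraction r of the standardised gap reaches the result. With SD 5.44, a gap of 1.1 flares is 1.1 / 5.44 = 0.20 SD, which moves the effect size by 0.06 SD at r = 0.3 and 0.12 SD at r = 0.6.

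Over repeated randomisations the shift has SD r × 0.289, which is 0.06 at r = 0.2 and 0.17 at r = 0.6. The chance that it exceeds 0.2, the smallest effect size in section 10.1, is 0.05% at r = 0.2, 2% at 0.3, 17% at 0.5 and 25% at 0.6.

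**5. The stratification factor.** The pooled SD exceeds the within-stratum SD by a factor √(1 + q(1 − q)D²). At q = 0.05 and D = 0.3 this is 1.002. At q = 0.20 and D = 0.8 it is 1.050. The excess is therefore about 0.2% to 5%.

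**6. What the residual SD would mean for phase III.** As an illustration, take effect size 0.2 on the raw SD scale, two-sided 5% and 80% power. The size per arm is 2 × (1.96 + 0.84)² × (1 − r²) / 0.2², using unrounded normal quantiles. This gives 393 unadjusted, 377 at r = 0.2, 295 at r = 0.5 and 252 at r = 0.6.

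**The case against.** The choice in section 10.5 is explicit and reasoned. The primary outcome is the proportion completing the trial, and flares are a secondary signal summarised by means and SDs. Several stronger readings are tempting, but the protocol does not support them.

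- **That the flare comparison is biased.** It is not. Under randomisation, analysed by intention to treat (section 10.7), chance imbalance is ordinary sampling error. The stratification factor should already be close to balanced by design.
- **That the standard errors ignore the stratified design.** Section 10.3.3 names no standard error, interval or test, so no stated error rate is invalidated.
- **That phase III would be undersized.** A raw SD larger than the residual SD makes phase III larger. It is also the right input if phase III is analysed unadjusted, and the protocol does not say which it will be.
- **That a 48% chance of a 1.1-flare imbalance could imitate the contrast in section 2.** That probability uses only the larger SD; with the smaller one it is about 15%. A baseline gap enters the result only in proportion to r. The outcome also covers weeks 5 to 28, not 12 months.
- **That adjustment is forbidden.** The wording is of intent. A later adjusted estimate remains possible, though it may carry the post hoc label, and section 14.1 promises public participant-level data.

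All of this stands, and it limits the consequences. It does not supply a reason to leave the information unused. Being a feasibility study is a weak reason when two of its objectives are to look for a flare signal and to size the next trial. A short baseline list is weak evidence by itself, since the SAP may extend it; the omission matters here only because the same two variables are left out of the analysis.

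**Conclusion.** The point holds as a minor one. The planned effect size is valid but less precise than the collected data allow, and the plan does not pre-specify the residual SD that an adjusted phase III would need. The total of 60 and the primary outcome do not change.

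The size of the gain rests on a correlation that the protocol does not give. At r = 0.2 it is negligible; at r = 0.5 to 0.6 the variance falls by a quarter to a third or more. Even then the signal stays imprecise. The allopurinol stratum contributes little over the assumed range. The case for change therefore rests mainly on prior flares, and on supplying the design figure for phase III.

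**What to change.** Keep the unadjusted summary in section 10.3.3 and replace section 10.5 with wording such as: *An exploratory estimate of the flare difference, with a 95% confidence interval, will be adjusted for the stratification factor (allopurinol contra-indicated, yes or no) and for the number of flares in the previous 12 months. Both the unadjusted SD and the residual SD (or dispersion, if a count model is used) will be reported for sizing phase III.* Add both variables to the list in section 10.3.1.

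The cost is a few sentences, no new data and about two degrees of freedom out of roughly 48 to 60 participants. If very few participants have a contra-indication, the stratum term may be uninformative: at a 5% share, 24 per arm gives 0.05 × 24 = 1.2 people per arm. The text should say that the term will be dropped, and the fact reported, if the stratum is too small to fit. The change should be made before unblinding so that the estimate is not post hoc.

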10.6 Interim analysis and criteria for the premature termination of the trial

As the main purpose of this study is to determine the metrics of an adequately powered definitive trial we will not perform any interim analysis. This is also given the fact that omega-3 fatty acids are safe, low-risk, and do not carry risk of serious adverse events.

10.7 Subject population

As this is a feasibility study, with feasibility outcomes, data for all randomised population will be analysed. When estimating a signal for efficacy of the drug, an intention to treat analysis will be performed.

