The proportion of DHA and EPA in plasma phospholipid increased from 2.79% at baseline to 6.20%, 8.26% and 9.78% after supplementation with 1.5 gm, 3.0 gm and 6.0 gm omega 3 fatty acids per day (41). The anti-inflammatory effects of omega-3 fatty acids assessed by endotoxin stimulated IL-1, and TN- α secretion become apparent in 4 weeks and increase over time (39, 40). The amount of omega-3 fatty acids in usual diet is unlikely to have such a strong anti-inflammatory effect (42).

In summary, these findings suggest that anti-inflammatory doses of omega-3 fatty acids DHA and EPA has a biological effect in human beings, and as they inactivate TLRs, NALP-3 inflammasome activity, neutrophil chemotaxis, and reduce prostaglandin levels, it is likely that they will have a specific effect in preventing flares of gout. However, omega-3 fatty acids cannot be used to treat episodes of acute gout as their anti-inflammatory effects takes four weeks to be established, and for this reason their effects on prophylaxis of acute gout may also be only apparent after four weeks (39, 40).

Preliminary data regarding effects of omega 3 fatty acids on gout flare frequency

Omega-3 fatty acid levels were measured in the serum of 112 community dwelling men with primary gout who also self-reported their flare frequency in the preceding 12 months. People with plasma omega-3 fatty acid level >0.40 mmol/L were less likely to report >2 flares of gout in the preceding 12 months independent of age, disease duration, BMI, tophi, and current serum uric acid (aOR (95%CI) 0.27 (0.09-0.76), p=0.014) (24).

CONFIDENTIAL

Page 24 of 77

IRAS: 240464

Eudra CT number 2018-000963-99

Apart from this, baseline data from an ongoing Arthritis Research UK funded clinical trial of nurse led package of care for gout (n=516) showed that the 27 patients on omega-3 fatty acid supplements at the time of the baseline visit reported fewer flares of gout in the preceding 12 months than those not taking these supplements (mean (standard deviation (S.D.) number of gout flares 3.07 (2.62) vs. 4.17 (5.44)), p=0.06 (equal variances not assumed) (Unpublished data [name]). We feel that the preliminary data is sufficient to justify a feasibility study.

Steady state plasma concentration

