3.2 Outcome

Primary outcome measure: Proportion of randomized patients completing the trial

Secondary outcome measures:

 proportion of patients approached by the GP with information about the study and requested to return the reply slip to the study team, who actually

CONFIDENTIAL

Page 28 of 77

IRAS: 240464

Eudra CT number 2018-000963-99

- i. reply to Academic Rheumatology, University of Nottingham
- ii. meet the eligibility criteria
- iii. agree for screening visit
- iv. meet the eligibility criteria after checking serum uric acid and other blood tests
- v. participate in the trial
- completeness of outcome data for each flare of gout
- number of gout flares between weeks 5 and 28*
- severity of flares of gout
- duration of flares of gout
- proportion of patients who withdraw from the study due to side effects related to omega-3 fatty acids
- number of gout patients not on ULT at each GP surgery as this will allow us to decide the number of GP surgeries in the main trial
- compliance with study drugs

*Gout flares between weeks 1 and 4 will be disregarded as the anti-inflammatory effects of omega-3 fatty acids take up to 4 weeks to manifest. However, this data will be collected so that it can be analysed in the proposed study.

CONFIDENTIAL

Eudra CT number 2018-000963-99

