10.8 Procedure(s) to account for missing data

CONFIDENTIAL

Page 56 of 77

IRAS: 240464

Eudra CT number 2018-000963-99

As this is a feasibility study, with quality of data as an outcome measure, we will not impute for missing data.

10.9 Other statistical considerations.

All deviations from previously agreed statistical analysis plan will be reported as post-hoc analysis.

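### The flare comparison uses raw counts with no term for time observed, so incomplete follow-up carries into the effect size meant for phase III planning

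*Protocol*

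**What the plan says.** Section 3.2 lists as a secondary outcome the "number of gout flares between weeks 5 and 28", a window of 24 weeks from day 29. Section 10.3.3 sets the estimator: "Mean difference in number of flares between the two arms, and pooled SD will be used to estimate the effect size of the intervention".

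Section 10.7 has data from everyone randomised analysed, and for efficacy states: "When estimating a signal for efficacy of the drug, an intention to treat analysis will be performed". Section 10.8 says "we will not impute for missing data", because data quality is itself an outcome. On numbers, section 10.1 reads: "we propose to include 60 participants (allowing for a c. 20% drop out rate) in this study". Section 4 gives "Randomisation: 1:1", so 30 per arm.

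No section mentions a flare rate, person-time or an offset. Three provisions limit missing data. Section 7.9 lets participants who stop study treatment continue with assessments if willing. Section 7.7 still invites those who discontinue to the final visit. Section 11.1 has incomplete data chased by telephone.

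**The concern.** A count depends on how long it was collected. The protocol expects some participants to leave, compares counts rather than rates, and does not fill in what is missing. That leaves two ways to handle a participant seen for part of the window. Either the truncated count goes into the mean as though it covered 24 weeks, or the participant drops out of the comparison.

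Under the first, the arm that loses more follow-up appears to have fewer flares. Under the second, the analysis covers available cases, and it is biased if people leave because of their flares and the arms differ in this.

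The comparison is secondary, but its results are deliverables. Objectives e and f in section 3.1 are the phase III sample size and a signal of effect, and section 10.1 justifies 60 participants partly by the wish to estimate the pooled SD.

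**Working it through.** **The plan's own figures.** Section 10.1 says 60 participants "will be able to estimate a dropout rate of 20% or higher to within a 95% confidence interval of +/- 10" percentage points. At 20% the half-width is 1.96 × √(0.20 × 0.80 / 60) = 0.101, so the figure reproduces there. Allowing for 20% dropout, 60 × 0.80 = 48 completers, or 24 per arm, so up to 12 participants may have incomplete flare data.

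**Inputs for illustration.** Section 2 gives flares in the previous 12 months for omega-3 supplement users versus non-users as mean (SD) "3.07 (2.62) vs. 4.17 (5.44". These are observational recall data from another trial. Scaled to 24 weeks:
- non-users: 4.17 × 24/52 = 1.92
- users: 3.07 × 24/52 = 1.42
- difference 0.51, rate ratio 0.74

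**Overdispersion.**
- Non-users: variance/mean = 5.44²/4.17 = 7.1; negative binomial k = 4.17²/(5.44² − 4.17) = 0.68.
- Users: variance/mean = 2.62²/3.07 = 2.2; k = 3.07²/(2.62² − 3.07) = 2.5.

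Both exceed the Poisson value of 1. The SD exceeds the mean only among non-users.

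**Truncated counts.** Suppose a proportion d of an arm drops out, with timing uniform over the window. Dropouts are then seen for half of it on average, and the expected raw count is the full count × (1 − d/2).
- No drug effect, 30% dropout on omega-3 and 10% on placebo: count ratio 0.85/0.95 = 0.89, a difference of 1.92 × (0.95 − 0.85) = 0.19 flares. Reversed: 0.95/0.85 = 1.12.
- True difference 0.51, 20% in each arm: 0.51 × 0.90 = 0.46, a 10% loss.
- 30% placebo, 10% omega-3: 1.92 × 0.85 − 1.42 × 0.95 = 0.29.
- 10% placebo, 30% omega-3: 1.92 × 0.95 − 1.42 × 0.85 = 0.62.

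**Alternatives, by simulation** (400,000 per arm, dispersion 1/k = 1.46 in both arms, true difference 0.51, true rate ratio 0.74). 'Unrelated' means dropout is independent of flares; 'related' means it rises with flare propensity.

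| Dropout, placebo / omega-3 | Complete-case difference, unrelated | Complete-case difference, related | Rate ratio per time observed, unrelated | Rate ratio per time observed, related |
|---|---|---|---|---|
| 20% / 20% | 0.50 | 0.42 | 0.74 | 0.74 |
| 30% / 10% | 0.51 | 0.06 | 0.73 | 0.81 |
| 10% / 30% | 0.52 | 0.77 | 0.73 | 0.67 |

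**Effect on planning** (dropout unrelated to flares; two-sided 5% alpha and 80% power are assumptions, since the protocol states neither for flares). With full follow-up the standardised difference is about 0.21 and the main trial needs about 350 to 360 per arm. From truncated counts:
- 20%/20%: 0.198, about 400 per arm
- 30%/10%: 0.129, about 943 per arm
- 10%/30%: 0.272, about 213 per arm

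In the balanced case the pooled SD also shrinks, from 2.42 to 2.30, so the standardised effect falls by only about 6%.

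**Against sampling error.** With no effect, the simulated pooled SD of truncated counts is about 2.57. The standard error of the difference at 30 per arm is 2.57 × √(2/30) = 0.66. The 0.19-flare bias is therefore about 0.3 standard errors.

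**The case against.** A reader might infer that intention to treat, no imputation and a raw mean difference contradict each other. The protocol does not support that. Intention to treat can mean analysis by allocated arm whatever was taken, as opposed to the per-protocol set mentioned in section 4. An unimputed comparison of those with data is then a familiar available-case version, and the label needs qualifying rather than withdrawing.

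Other points on that side also stand:
- Section 10.1 expects about 20% to drop out, not 20% to lack flare data. With the follow-up offered in sections 7.7, 7.9 and 11.1, 12 of 60 is close to an upper bound. Section 7.9 also says that poor tolerability alone is no reason for withdrawal.
- Equal dropout in amount and timing gives no bias when there is no effect. The 30%/10% split is assumed, and its bias is well inside sampling error.
- Mean difference and pooled SD serve the stated aim of estimating the SD for planning.
- The rule for partial counts may sit in an analysis plan not shown; section 10.9 refers to one.

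The last point does not dispose of the matter. Section 10.3.3 itself chooses an estimator with no term for time observed, and the follow-up provisions reduce missing data without saying how a partial count enters the mean.

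**Conclusion.** The point holds as a weakness that should be corrected in a secondary analysis. The primary outcome, completion of the trial, is unaffected. Followed as written, the flare comparison either treats truncated counts as full ones or becomes available-case.

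The sizes rest on uniform dropout timing, on section 2 recall rates scaled to 24 weeks, and on dropout splits that the documents do not give. On those terms the true difference loses about 10% with balanced 20% dropout, and the null count ratio is about 0.89 or 1.12 with a 30%/10% split.

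A reader might conclude that a false efficacy signal is likely. The documents do not show this: no efficacy test is specified, differential dropout is only a possibility, and sampling noise dominates at this size. The practical harm is a distorted effect size carried into phase III planning. Nor can the section 2 data be described as having an SD above the mean throughout; that is true of one group, although both are overdispersed.

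**What to change.** In sections 10.3.3, 10.7 and 10.8:
- Add a negative binomial analysis of flares from day 29 to last contact or week 28, with log observed weeks as offset, by allocated arm, in all randomised participants with any time at risk.
- Report the rate per 24 weeks by arm, the rate ratio with 95% CI, the dispersion parameter and observed follow-up time by arm.
- Report by arm the number with no follow-up after day 28, because the offset model cannot include them either.
- Keep the mean difference and pooled SD as descriptive planning figures.

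An offset is not covariate adjustment, so section 10.5 can stand. The cost is a few sentences and a standard command in the Stata package named in section 4. The change should be made before analysis, since section 10.9 treats departures from the agreed plan as post hoc.

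The limitation to state is that the model assumes data missing at random. If dropout is related to flares and differs by arm, bias remains: in the illustration the rate ratio became 0.81 or 0.67 against a true 0.74.
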